5.5.2 Rationale for Dosing Schedule

5.5.2.1 BMS-986207

In this study, the BMS-986207 dosing schedule of q2w was based on the projected human half-life, derived from a monkey single dose study [REDACTED]. The PK profiles of BMS-986207 in monkeys following a single IV dose of 1, 10, and 100 mg/kg were used to project the human PK

parameters. The projected half-life in humans is [REDACTED], which approximates 14 days (q2w), the selected dosing schedule.

The human effective dose of BMS-986207 administered in combination with nivolumab in cancer patients, was projected to target steady-state average plasma concentration (C_{ave}) and minimum plasma concentration (C_{min}) of [REDACTED] [REDACTED], respectively, equivalent to 10A7-mIgG1 D265A C_{ave}_14d and C_{min}_14d at the efficacious dose in CT26 mouse tumor model. Based on the projected human PK of BMS-986207, the human effective is projected to be 4 mg/kg IV administered once every 2 weeks (q2w). A flat dose of BMS-986207 (mg) will be used in this study, given similar exposure variability of flat-dose as compared to body weight-based dosing for many therapeutic antibodies and practical advantages.⁴¹

The current protocol evaluates the q2w dosing regimen. A dosing regimen of q4w is being considered for the single-agent of BMS-986207, as well as with in combination with nivolumab. The q4w option will benefit the patients with less frequent visits and reduce the medical burden from the care givers and the cancer treatment institutions. The projected human PK profile of BMS-986207 is linear, and the dose for q4w dosing schedule will be based on q2w with linear extrapolation. The exposure, efficacy and safety, of BMS-986207 as a single agent and in combination with nivolumab, will be evaluated and compared with the q2w dosing schedule. Based on the totality of clinical data, the sponsor will consider to revise the dosing regimen, if appropriate.

BMS-986207 PK was evaluated in participants with advanced solid tumors receiving q2w (20, 80, 240, 800, or 1600 mg) and q4w (480 or 1600 mg) doses in Part 1A, 1B and 2A of CA020002. Preliminary PK results of BMS 986207 suggest the increase in exposure is proportional across the dose range evaluated, which is in agreement with preclinical predictions. The CLT appears consistent across doses. For participants who received combination treatment with nivolumab in Part 1B, the PK of BMS-986207 appears to be consistent with that reported for monotherapy in Part 1A and 2A.¹⁹

In the Triplet Cohort (Part 1C), the initial proposed BMS-986207 dose was 1200 mg q3w based on lower C_{max}, similar C_{avg} and [REDACTED] as compared to 1600 mg q4w, a safe and tolerable dose evaluated in combination with nivolumab in Part 1B and the projected saturation of intratumoral TIGIT receptor occupancy at [REDACTED] level to provide optimal clinical benefit. Preliminary data as per 20-Oct-2021, revealed that 2 out of 4 DLT-evaluable participants experienced DLTs with the combination of BMS-986207 1200 mg Q3W, nivolumab 360 mg Q3W, and ipilimumab 1 mg/kg Q6W (see [Section 3.2.1.4](#) for more details). BMS-986207 dose of 1200 mg Q3W was reduced to 600 mg per BOIN design. BMS-986207 dose of 600 mg Q3W is expected to provide half of the exposure as compared to 1200 mg Q3W, and a relatively high intratumoral TIGIT receptor occupancy at the [REDACTED] level. In addition, BMS-986207 dose of 360 mg Q3W may be explored to aid in RP2D dose selection and per BOIN design if de-escalation is needed.

The selection of an every-3-weeks regimen allows for aligning the schedule of BMS-986207 with combination of nivolumab q3w and ipilimumab q6w in 1L NSCLC (See [Section 5.5.2.2](#) and

Section 5.5.2.3), since the primary efficacy evaluation in Part 2C will be in participants with 1L NSCLC.

5.5.2.2 *Nivolumab*

Nivolumab monotherapy has been extensively studied in multiple tumor types, including melanoma, NSCLC, RCC, cHL, SCCHN, and urothelial carcinoma, and has been safely administered at doses up to 10 mg/kg q2w. Nivolumab is currently approved for the treatment of various tumor types with monotherapy regimen of 480 mg q4w, 240 mg q2w, or 3 mg/kg q2w. When used in combination with ipilimumab and chemotherapy, nivolumab 360 mg q3w is approved for the treatment of 1L NSCLC.

Based on the clinical experience and quantitative clinical pharmacology understanding, nivolumab 480 mg q4w, 360 mg q3w, or 240 mg q2w infused over approximately 30 minutes were selected in this study as these doses are expected to provide similar nivolumab exposures (Cavg and Ctrough), and to allow the flexibility of aligning doses of nivolumab at the same dosing frequency of BMS-986207 for the combination treatment.

Specifically, in the Triplet Cohort (Part 1C) and Triplet NSCLC Expansion (Part 2C), participants will receive 360 mg q3w nivolumab in combination with ipilimumab 1 mg/kg q6w and BMS-986207 600 mg q3w.

5.5.2.3 *Ipilimumab*

Ipilimumab is approved as monotherapy for the treatment of advanced melanoma and adjuvant melanoma with 3 mg/kg q3w for 4 doses and 10 mg/kg q3w for 4 doses followed by maintenance dose, respectively. Ipilimumab is also approved in combination with nivolumab for the treatment of various cancers, including melanoma, RCC, CRC, and HCC with a dosing regimen of 1 mg/kg q3w or 3 mg/kg q3w for 4 doses, depending on tumor type.²²

In addition, a less frequent but continuous ipilimumab regimen (1 mg/kg q6w) is being evaluated in combination with nivolumab or nivolumab plus chemotherapy in a number of pivotal studies, including 1L NSCLC studies CA209227 and CA2099LA, 1L SCCHN study CA209651, and 1L mesothelioma study CA209743. For instance, study CA2099LA, evaluating nivolumab 360 mg q3w plus ipilimumab 1 mg/kg q6w given concomitantly with 2 cycles of chemotherapy, demonstrated superior survival benefit to patients with 1L NSCLC as compared to SOC chemotherapy. The safety profile of this triple combination regimen was reflective of the known safety profiles of the immunotherapy and chemotherapy. Ipilimumab 1 mg/kg q6w is currently approved for the treatment of 1L NSCLC, in combination with nivolumab or with nivolumab and 2 cycles of chemotherapy, and is also approved for the treatment of 1L mesothelioma, in combination with nivolumab.³⁴

Based on the clinical experience, low-dose ipilimumab 1 mg/kg q6w infused over approximately 30 minutes will be examined in combination with nivolumab and BMS-986207 in the Triplet Cohort (Part 1C) and Triplet NSCLC Expansion (Part 2C) of this study.

5.5.2.4 Rationale for Infusion Times

Long infusion times (greater than or equal to 60 minutes), especially when multiple agents are administered sequentially to an individual, place a burden on participants and treatment centers. Establishing that investigational agents, such as BMS-986207, can be safely administered using an infusion time of 60 minutes will diminish the burden, provided there is no change in the safety profile.

In addition, a 60-minute post infusion safety observation period is considered appropriate given BMS-986207 is a fully human monoclonal antibody that is an antagonist (not an agonist) and has a low likelihood of resulting in infusion reactions. For participants < 42 kg on the 1600 mg dose, the infusion time will be 90 minutes. Details of drug preparation are found in Pharmacy Manual, a document that will be provided separately to the site.

In Parts 1B and 2B, when both study drugs are given in combination, nivolumab will be given first, over a 30 minute infusion period, followed by BMS-986207 over a 60-minute infusion period, beginning at least 30 minutes after completion of the infusion of nivolumab.

Nivolumab has been administered safely over 60 minutes at doses ranging up to 10 mg/kg over long treatment duration. In Study CA209010 (a Phase 2, randomized, double-blinded, dose-ranging study of nivolumab in participants with advanced/metastatic clear cell RCC), a dose association was observed for infusion site reactions and hypersensitivity reactions (1.7% at 0.3 mg/kg, 3.7% at 2 mg/kg, and 18.5% at 10 mg/kg). All the events were Grade 1 to 2 and were manageable. An infusion duration of 30 minutes for 3 mg/kg nivolumab (30% of the dose provided at 10 mg/kg) is not expected to present any safety concerns compared to the prior experience at 10 mg/kg nivolumab dose infused over a 60 minute duration.

Similarly, ipilimumab, which will be given in Part 1C and Part 2C, was safely administered over 90 minutes at 10 mg/kg. In the CA184022 study, where ipilimumab was administered up to a dose of 10 mg/kg, on-study drug related hypersensitivity events (Grade 1-2) were reported in 1 (1.4%) participant in the 0.3 mg/kg group and in 2 (2.8%) participants in the 10 mg/kg group. There were no drug-related hypersensitivity events reported in the 3 mg/kg group. Across the 3 treatment groups, no Grade 3-4 drug-related hypersensitivity events were reported and there were no reports of infusion reactions. Ipilimumab 10 mg/kg monotherapy has also been safely administered as a 90 minute infusion in large phase 3 studies in prostate cancer (CA184043) and as adjuvant therapy for stage 3 melanoma (CA184029), with infusion reactions occurring in participants. Administering 1 mg/kg of ipilimumab represents one-tenth of the 10 mg/kg dose and will be administered over one-third of the time, for a lower infusion rate.

Of note, CA209153, a Phase 3b/4 safety study of nivolumab in participants with metastatic NSCLC who have progressed during or after at least 1 prior systemic regimen, used a 30 minute infusion in a cohort of participants with no safety issues.

Overall, infusion reactions, including high-grade hypersensitivity reactions, have been uncommon with nivolumab or ipilimumab administration or the combination of nivolumab and ipilimumab. Overall, a change in safety profile is not anticipated with a 30-minute infusion of nivolumab or ipilimumab, infusion times that are consistent with the current USPIs for each drug.

For participants with a bodyweight of > 250 kg the dosing of BMS-986207 will occur the day after dosing of nivolumab and ipilimumab when these drugs are administered on the same day. Details of study drug preparation are found in the Pharmacy Manual, a document that will be provided separately to the site.

6. STUDY POPULATION

For entry into the study, the following criteria MUST be met prior to dosing on Day 1. No exceptions will be granted. This study permits the re-enrollment of a participant that has discontinued the study as a pretreatment failure. If re-enrolled, the participant must be re-consented and meet all inclusion/exclusion criteria.

6.1 Inclusion Criteria

- 1) Signed Written Informed Consent
 - a) The participant must sign the ICF prior to the performance of any study-related procedures that are not considered part of standard of care.
 - b) The participant must sign the consent for pretreatment and on treatment [REDACTED] (See [REDACTED] for details).
- 2) Target Population
 - a) Participants must be at least 18 years old and have histologic or cytologic confirmation of a solid tumor that is advanced (metastatic, recurrent and/or unresectable) with measurable disease per RECIST v1.1 ([Appendix 5](#)).
 - b) Eastern Cooperative Oncology Group (ECOG) Performance Status of 0 or 1 ([Appendix 8](#))
 - c) All solid tumor histologies will be permitted in Parts 1A, 1B, and 1C
 - d) Parts 1A, 1B, and 1C, participants must have received, and then progressed or been intolerant to, at least 1 standard treatment regimen in the advanced or metastatic setting, if such a therapy exists.
 - e) Part 1A, participants with tumor types where the microbiome has been hypothesized, based on preclinical or clinical data, to mediate TIGIT inhibition (such as, but not limited to, CRC and SCCHN), will be prioritized for enrollment
 - f) Part 1B, participants with tumor types where PD1/PD-L1 inhibitors are indicated as front line treatment can be enrolled to this study treatment naïve
 - g) Part 2 A, only participants with CRC
 - h) Part 2 B, only participants with CRC, HCC and ovarian cancer,
 - i) Participants with CRC must have received, and then progressed on or have been intolerant or refractory to, at least 1 standard systemic therapy for metastatic and/or unresectable disease (or have progressed within 6 months of adjuvant therapy).
 - j) Participants with CRC, microsatellite instability (MSI), mismatch repair (MMR), V-Ki-ras2 Kirsten rat sarcoma viral oncogene homolog (KRAS), and B-Raf proto-oncogene (BRAF) status, if known, should be documented. If unknown, participants must consent to allow their submitted archived tumor tissue sample (block or unstained slides) to be tested.

- k) For Part 2B Participants with HCC must have advanced HCC not amenable to curative resection, ablation or liver transplant.
- l) For participants with HCC who progressed after locoregional therapy, then locoregional therapy must be completed at least 4 weeks prior to the baseline scan. All acute toxic effects of any prior local treatment must have resolved to NCI CTCAE v4.03 Grade ≤ 1 or been deemed irreversible
- m) Participants with radiological diagnosis of HCC may be enrolled for screening in the study but histological confirmation of HCC is mandatory prior to initiation of study therapy.
- n) For participants with HCC, previous progressive disease, or been intolerant to, at least 1 line of therapy or refused treatment with sorafenib
- o) For participants with HCC A Child-Pugh Class A (6 points or less) ([Appendix 11](#))
- p) For participants with HCC Must have results of testing for hepatitis B surface antigen, hepatitis B surface antibody, hepatitis B core antibody, hepatitis B DNA polymerase chain reaction (PCR), hepatitis C antibody and hepatitis C ribonucleic acid (RNA) PCR.
- q) For HCC participants with hepatitis B infection, a hepatitis B DNA viral load < 100 IU/mL is required and the participant must be on anti-viral therapy per institutional guidelines
- r) For participants with hepatitis B infection, there must be no co-infection with hepatitis C or hepatitis D (must obtain hepatitis D antibody testing)
- s) For participants with hepatitis C infection (HCV), active HCV infection, as defined by any detectable HCV RNA and positive antibody, can be enrolled providing they are on anti-viral therapy. Resolved HCV infection, as evidenced by undetectable HCV RNA and positive antibody, can be enrolled. Participants on antiviral therapy for HCV are permitted to enroll in the study and should continue treatment during the study. Participants with active HCV who are not on antiviral therapy at screening cannot be enrolled in the study
- t) For participants with ovarian cancer in Part 2B, histologically or cytologically documented epithelial ovarian cancer, primary peritoneal carcinoma, or fallopian tube cancer
- u) For participants with ovarian cancer in Part 2B completed at least one platinum based therapy (PBT) regimen (carboplatin, cisplatin, or another organoplatinum compound)
- v) For participants with ovarian cancer in Part 2B, with platinum refractory, resistant, sensitive, intolerance to PBT (inability to receive PBT due to hypersensitivity reactions to platinum) are eligible
- w) Part 2C, only participants with NSCLC who are treatment naive with baseline tumor PD-L1 expression $\geq 1\%$ are eligible
 - i) Participants with NSCLC in Part 2C must have histologically confirmed NSCLC per the 8th International Association for the Study of Lung Cancer classification (IASLC) of squamous or non-squamous histology, with no prior systemic anti-cancer therapy

(including epidermal growth factor receptor (EGFR) and anaplastic lymphoma kinase (ALK)/ROS1 inhibitors) given as primary therapy for advanced or metastatic disease.

- ii) Prior definitive chemoradiation for locally advanced disease is permitted as long as the last administration of chemotherapy or radiotherapy (which ever was given last) occurred at least 6 months prior to enrollment.
- iii) Prior adjuvant or neoadjuvant chemotherapy is permitted as long as the last administration of the prior regimen occurred at least 6 months prior to enrollment.
- iv) Measurable disease by CT or MRI per RECIST v1.1 criteria ([Appendix 5](#)); radiographic tumor assessment performed within 28 days before randomization
- v) Target lesions may be located in a previously irradiated field if there is documented (radiographic) disease progression in that site after the completion of radiation therapy.
- vi) A formalin-fixed, paraffin-embedded (FFPE) tumor tissue block (preferred) or a minimum of 20 unstained slides of tumor tissue from core biopsy, excisional or incisional biopsy obtained during screening or prior to enrollment (within 3 months of enrollment and with no intervening systemic anti-cancer treatment between time of acquisition and enrollment) must be sent to the central laboratory. Fine needle aspirates or other cytology samples are not acceptable. Biopsies of bone lesions that do not have a soft tissue component or decalcified bone tumor samples are also not acceptable.
- vii) Participants must have pre-existing or prior PD-L1 immunohistochemistry (IHC) results within 3 months of enrollment from testing of tumor tissue. PD-L1 expression must be tumor cell positive $\geq 1\%$ for a participant to be eligible for enrollment.
- viii) Prior palliative radiotherapy to non-CNS lesions must have been completed at least 2 weeks prior to randomization. Participants with symptomatic tumor lesions at baseline that may require palliative radiotherapy within 4 weeks of randomization are strongly encouraged to receive palliative radiotherapy prior to treatment assignment.

3) Physical and Laboratory Test Findings

- a) Adequate hematologic function for participants as defined by the following:
 - i) Neutrophils $\geq 1500/\mu\text{L}$
 - ii) Platelets $\geq 100 \times 10^3/\mu\text{L}$ (transfusion to achieve this level is not permitted within 2 weeks of first study drug administration)
 - iii) Hemoglobin $\geq 9 \text{ g/dL}$ (transfusion to achieve this level is not permitted within 2 weeks of first study drug administration)
 - iv) WBC $> 2000/\mu\text{L}$
- b) Adequate hepatic function (except for HCC)
 - i) Alanine aminotransferase (ALT) and aspartate aminotransferase (AST) $\leq 3 \times$ upper limit of normal (ULN)

- ii) Total bilirubin $\leq 1.5 \times$ ULN (except participants with Gilbert's Syndrome who must have normal direct bilirubin)
- iii) **Specifically for participants with HCC:**
 - (1) Prothrombin time-international normalized ratio (PT/INR) ≤ 2.3 or PT ≤ 6 seconds above control
 - (2) Adequate hepatic function as documented by:
 - (a) Serum albumin ≥ 2.8 g/dL
 - (b) Total bilirubin ≤ 3 mg/dL
 - (c) AST and ALT $\leq 5 \times$ the institutional ULN
- c) Clinically stable thyroid function per Investigator assessment.
- d) Serum creatinine $\leq 1.5 \times$ ULN or creatinine clearance (CrCl) ≥ 40 mL/min (measured using the Cockcroft-Gault formula below):

$$\text{Female CrCl} = \frac{(140 - \text{age in years}) \times \text{weight in kg} \times 0.85}{72 \times \text{serum creatinine in mg/dL}}$$

$$\text{Male CrCl} = \frac{(140 - \text{age in years}) \times \text{weight in kg} \times 1.00}{72 \times \text{serum creatinine in mg/dL}}$$

- e) Ability to comply with treatment, PK and PD sample collection and required study follow-up periods
- 4) Age and Reproductive Status
 - a) Males and females, aged at least 18 years old or local age of majority.
 - b) Women of childbearing potential (WOCBP) must have a negative serum or urine pregnancy test (minimum sensitivity of 25 IU/L or equivalent units of human chorionic gonadotrophin) within 24 hours prior to the first dose of study drug.
 - i) If a urine test cannot be confirmed as negative (eg, an ambiguous result), a serum pregnancy test is required. In such cases, the participant must be excluded from participation if the serum pregnancy result is positive.
 - ii) Additional requirements for pregnancy testing during and after study intervention are located in [Section 2](#), Schedule of Activities.
 - iii) The investigator is responsible for review of medical history, menstrual history, and recent sexual activity to decrease the risk for inclusion of a woman with an early undetected pregnancy.
 - c) Women must not be breastfeeding
 - d) WOCBP must agree to follow instructions for method(s) of contraception defined in [Appendix 4](#) and as described below (g) and included in the ICF.

- e) WOCBP who are continuously not heterosexually active are also exempt from contraceptive requirements, but should still undergo pregnancy testing as described in this section.
- f) Male participants should maintain their usual practice with regard to contraception (if any); however, no specific contraceptive measures are required.
- g) Please see [Appendix 4](#) for further information on contraception methods.
- h) WOCBP are permitted to use hormonal contraception methods (as described in [Appendix 4](#))
 - i) A female participant is eligible to participate if she is not pregnant or breastfeeding, and at least 1 of the following conditions applies:
 - (1) Is not a WOCBP
 - OR
 - (2) Is a WOCBP and using a contraceptive method that is highly effective (with a failure rate of < 1% per year), preferably, with low user dependency, as described in [Appendix 4](#) during the intervention period and for at least 5 months and agrees not to donate eggs (ova, oocytes) for the purpose of reproduction for the same time period
 - j) Female participants must have documented proof that they are not of childbearing potential.
 - j) Women who are not of childbearing potential are exempt from contraceptive requirements.

Investigators shall counsel WOCBP, and male participants who are sexually active with WOCBP, on the importance of pregnancy prevention and the implications of an unexpected pregnancy.

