3.2.4 Nivolumab Combined with Ipilimumab Clinical Activity

Multiple clinical studies have evaluated nivolumab combined with ipilimumab at different doses and schedules. Based on Phase 3 data showing improved survival over standard-of-care therapies, nivolumab combined with ipilimumab has been approved in multiple countries for the treatment of patients with unresectable or metastatic melanoma, intermediate or poor risk, previously untreated advanced RCC, previously untreated metastatic NSCLC expressing [REDACTED] and microsatellite instability-high or mismatch repair deficient colorectal cancer. Details of the clinical activity in these various malignancies are provided in the USPI and SmPC.^{34,20}

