5.4.7 Rationale for Tumor Selection

TIGIT is expressed by activated T cells, Tregs, and NK cells, and binds the adhesion molecules PVR (CD155) and Nectin-2 (CD112) with higher and lower affinity, respectively.¹³ PVR and Nectin-2 also bind to TIGIT's co-stimulatory counterpart, DNAM-1 (CD226). DNAM-1 is an activating receptor expressed on NK cells, CD8+ T cells, and other immune cells.⁴⁰ Upon recognizing its ligands PVR and Nectin-2, DNAM-1 promotes NK cell-mediated elimination of damaged cells.

One can hypothesize that the tumors most likely to respond to anti-TIGIT therapy are those with the highest PVR/Nectin-2 expression, and those with moderate-to-high immune cell infiltration. Accordingly, the selected tumor types of HCC, CRC, ovarian cancer, and NSCLC and their respective rationale for selection, are given in Table 5.4.7-1.

Table 5.4.7-1: Rationale for Tumor Selection

Rationale	Tumor Selection	Comments
1 • High ligand expression but low TILs • Aim to increase TILs and trigger anti-tumor activity • Potential for anti-TIGIT and nivolumab combination	HCC	
2 PD1 nonresponsive tumors with mechanistic rationale	CRC	TIGIT-mediated immune escape via microbiome. CRC, and other indications in which F. nucleatum may play a role in the immune escape, will be evaluated in TIGIT monotherapy and TIGIT + nivolumab.

Table 5.4.7-1: Rationale for Tumor Selection

Rationale		Tumor Selection	Comments
3	Nectin-centric tumor to differentiate role of nectin-2 and PVR	Ovarian cancer	Nectin-2 in ovarian cancer is the key driver of TIGIT-mediated immune suppression.
4	
 High ligand expression correlates with PD-L1 expression especially in TILs Potential for anti-TIGIT and anti-PD-L1/PD-1 antibodies combination in PD-L1-positive NSCLC. 	NSCLC	

Abbreviations: CRC, colorectal cancer; HCC, hepatocellular carcinoma; NSCLC, non-small cell lung cancer; PD-(L)1, anti-programmed cell death (ligand) 1; PVR, poliovirus receptor TIGIT, T cell Ig and ITIM domain; TIL, tumor infiltrating lymphocyte.

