10.1.3.1 Cohort Expansion in Part 2A and Part 2B

Part 2A will be an expansion phase of the BMS-986207 monotherapy in participants with CRC at 1 dose level. Part 2B will be an expansion phase for BMS-986207 in combination with nivolumab in participants with CRC, HCC, and ovarian cancer. Each disease cohort expansion will be handled independently and there will be no multiplicity adjustment.

The Fleming 2-stage design framework will be used as a guide for the expansion cohorts in Parts 2A and 2B.^{42,43} The total sample size for each expansion cohort will be calculated to provide a reasonable false-positive rate (FPR) <10% and false-negative rate (FNR) < 10% based on

assumptions of true (target) and historic ORR for each indication. The assumed historic and target response rates may change over time and may need to be adjusted by the time when the response data from this study are available. The sample size and operational characteristics of using a 2-stage design, as an example, are provided in Table 10.1.3.1-1, although this is not used for statistical hypothesis testing. Using a 2-stage design provides an option to stop early for futility, as well as a signal of preliminary [REDACTED] activity for strong-go, early on. Enrollment may continue into Stage 2, while the planned number of participants for Stage 1 are followed for efficacy evaluable tumor assessments. There will be no stopping of a disease cohort for efficacy, although an early plan for the next stage of clinical development may be initiated. Sample sizes may need to be increased in order to explore differential responses between [REDACTED] expressed and nonexpressed groups.

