Guided by Table 10.1.3.1-1, approximately 11 CRC participants will be treated with BMS-986207 monotherapy in Stage 1. Assuming the true response rate is 20% in this population when treated with BMS-986207 monotherapy, if there are 2 or more responses in 11 participants, it may trigger an expansion of the clinical development plan after careful evaluation of all available data including duration of response and safety profile. The probability to observe such a favorable response is approximately 68% if in fact the treatment is efficacious. If there is no response in 11 treated participants, the cohort may be stopped for futility. The probability of early stopping for futility is approximately 80% if in fact the treatment is inefficacious, eg, 2%. If there is 1 response, an additional 13 participants may be treated to collect more data. At the end of Stage 2, if there is 1 or no response, further clinical development may not be warranted. If there are 2 or more responses, it may show evidence of treatment efficacy.

Table 10.1.3.1-1: Example of a 2-stage Design Characteristics

Treatment	Indication	Historic/Target Rate (%)	Stage	Cum Sample Size	Conclude Inefficacy if R ^a	Conclude Efficacy if R ^a	PET ^b for Futility (%)	PEE ^c for Efficacy (%)
BMS-986207	CRC (nonMSI-H)	2/20	1	11	0	≥ 2	80	68
			2	24	≤ 1	≥ 2		
BMS-986207 and nivolumab	HCC, ovarian cancer	10/30	1	15	≤ 1	≥ 4	55	70
			2	26	≤ 5	≥ 6		
	CRC (nonMSI-H)	2/30	1	7	0	≥ 2	87	67
			2	15	≤ 1	≥ 2		

Abbreviations: BMS = Bristol-Myers Squibb, CRC, colorectal cancer; FNR, false-negative rate; FPR, false-positive rate; HCC, hepatocellular carcinoma; nonMSI-H, nonmicrosatellite instability-high; PEE, probability of early efficacy; PET, probability of early termination

^a R is the cumulative number of responses at the end of stage; all FPRs and FNRs < 10%

^b Probability of early termination if the historic rate is true

^c Probability of early efficacy signal if the target rate is true

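### The Part 2B colorectal design assumes non-MSI-H disease with a 2% historic response rate, but MSI-H/dMMR patients may enrol and are counted, so the stated false-positive rate below 10% is not secured in the nivolumab arm

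*Combined protocol and SAP*

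**What the plan says.** Table 10.1.3.1-1 (Section 10.1.3.1) gives the CRC row for BMS-986207 plus nivolumab as "CRC (nonMSI-H) 2/30 1 7 0 ≥ 2 87 67". That is a 2% historic and 30% target ORR, 7 participants in stage 1, futility at 0 responses and a signal at 2 or more. Stage 2 brings the total to 15, again with a signal at 2 or more. The text aims for a "reasonable false-positive rate (FPR) <10% and false-negative rate (FNR) < 10% based on" historic and target rates, and the table footnote repeats the claim for every row. The monotherapy CRC row is also labelled non-MSI-H.

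Section 5.4.7 selects CRC under the rationale "PD1 nonresponsive tumors with mechanistic rationale".

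Section 6.1 item 2)h reads "Part 2 B, only participants with CRC, HCC and ovarian cancer", with no molecular restriction. Item 2)j covers MSI, MMR, KRAS and BRAF: "status, if known, should be documented. If unknown, participants must consent to allow their submitted archived tumor tissue sample" to be tested. Section 6.2 has no MSI-H or dMMR exclusion, and it permits prior anti-PD-1/PD-L1 therapy without requiring it.

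Table 10.3.1-1 defines ORR over all treated participants and, for Parts 2A and 2B, reports it by treatment and tumour type. Table 10.2-1 has no non-MSI-H CRC set. It does have a central-laboratory PD-L1 set for the NSCLC cohort in Part 2C.

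Section 3.2.2 lists CRC among the tumours with durable responses to nivolumab alone. Section 3.2.4 reports that nivolumab plus ipilimumab is approved for "microsatellite instability-high or mismatch repair deficient colorectal cancer".

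**The concern.** The threshold was set for one population and will be applied to another. If every criterion is followed, a site may enrol an MSI-H/dMMR patient, and that patient's response counts towards the 2 that make a signal. By the protocol's own account, checkpoint inhibitors including nivolumab have activity in CRC, and a nivolumab-containing regimen is approved in this molecular subgroup. The 2% null therefore cannot be assumed for these patients once they receive nivolumab.

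With a threshold of 2, one or two such responses could look like activity of the added BMS-986207. The cohort would then say little about the question posed in Section 5.4.7, which is activity in CRC that does not respond to PD-1 blockade.

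**Working it through.** **Inputs from the plan (Table 10.1.3.1-1, CRC with nivolumab):** n1 = 7, total 15, stop at 0 of 7, signal at 2 or more, p0 = 0.02, p1 = 0.30.

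**Formula.** P(signal) = P(X1 ≥ 2) + P(X1 = 1) × P(X2 ≥ 1), with X1 ~ Bin(7, p) and X2 ~ Bin(8, p). Section 10.1.3.1 makes the futility stop optional and lets enrolment run on into stage 2. The single-stage value P(X ≥ 2 | 15, p) is therefore given as well, labelled no stop.

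**Reproducing the plan.**
- Early termination at 2%: 0.98^7 = 86.8% (plan 87%).
- Early signal at 30%: 1 − 0.7^7 − 7 × 0.3 × 0.7^6 = 67.1% (plan 67%).
- FPR at 2%: 0.0079 + 0.1240 × 0.1492 = 2.6%. No stop: 1 − 0.98^15 − 15 × 0.02 × 0.98^14 = 3.5%.
- False-negative rate (FNR) at 30%: 1 − (0.6706 + 0.2471 × 0.9424) = 9.7%. No stop: 3.5%.

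The row is correct for a pure non-MSI-H cohort.

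**Break-even.** Setting P(signal) = 10% and solving for p gives 4.2% (two-stage) or 3.6% (no stop).

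**Mixed cohort.** With MSI-H share s and MSI-H ORR q under nivolumab, the blended null is p = 0.02 × (1 − s) + q × s. Neither s nor q is in the documents; the values below are assumptions.

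Example, s = 5%, q = 30%: p = 0.019 + 0.015 = 0.034, and FPR = 0.0217 + 0.1934 × 0.2417 = 6.8%.

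| MSI-H share | Blended null (q = 30 / 40 / 50%) | FPR, two-stage | FPR, no stop |
|---|---|---|---|
| 2% | 2.56 / 2.76 / 2.96% | 4.1 / 4.7 / 5.4% | 5.5 / 6.3 / 7.1% |
| 5% | 3.4 / 3.9 / 4.4% | 6.8 / 8.7 / 10.6% | 9.1 / 11.4 / 13.9% |
| 10% | 4.8 / 5.8 / 6.8% | 12.3 / 16.6 / 21.2% | 16.0 / 21.5 / 27.2% |

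Share at which the two-stage FPR reaches 10%: (0.0425 − 0.02)/(q − 0.02), which is 12.5% for q = 20%, 8.0% for 30%, 5.9% for 40% and 4.7% for 50%.

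**Fixed number of MSI-H participants among 15 (q = 30 / 40 / 50%).**
- One, no stop: (1 − q) × 0.0310 + q × 0.2464 = 9.6 / 11.7 / 13.9%. Here 0.0310 and 0.2464 are the chances of at least 2 and at least 1 response among the other 14 at 2%.
- One, two-stage, entry order random: 7.2 / 8.8 / 10.4%.
- Two, two-stage: 15.2 / 21.3 / 28.4%. No stop: 20.0 / 28.1 / 37.2%.

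**The case against.** **The rule is only a guide.** Section 10.1.3.1 calls the table an example, says it is not used for hypothesis testing, and allows the historic rate to be revised. Section 3.1 says no hypotheses are formally evaluated. In the monotherapy example, two responses may prompt further development only after all data are reviewed. This stands and lowers the severity. A reader might infer that two MSI-H responses would force a go decision; the text does not say so. The counts are still the plan's stated guide, and Section 10.1.3 bases the cohort size on target versus historic ORR.

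**Status is recorded, so responders can be checked afterwards.** True, and the row label can be read as meaning that only non-MSI-H responses count. The protocol nowhere states that counting rule, however, and Table 10.3.1-1 points the other way. The separate SAP, redacted biomarker text or figures not shown could contain such a rule, but the eligibility and analysis text available here does not.

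**The size depends on outside figures.** Also true. At a 2% share the FPR stays at 4-5%. At a 5% share, a cohort of 15 has at most one MSI-H member about 83% of the time (0.95^15 + 15 × 0.05 × 0.95^14). The approval cited in Section 3.2.4 is with ipilimumab, which Part 2B does not give. Section 3.2.2 gives no response rate and no MSI breakdown. CRC entrants are pretreated, and some may already have had anti-PD-1 therapy. These facts argue for a wide range, not for a 2% null.

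**Conclusion.** The point holds at moderate severity for the nivolumab arm of Part 2B CRC. The FPR below 10% is right for the labelled population and is not secured for the population that may enrol. The slack is real: 2.6% by design, with 10% reached only when the blended null roughly doubles to 4.2% (3.6% without the stop). With an assumed MSI-H ORR of 30-50%, a 5% share brings the two-stage FPR to the neighbourhood of the limit and a 10% share takes it past.

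Three stronger readings are not supported:
- That the FPR does exceed 10%. This depends on a share and a response rate that the documents do not give.
- That MSI-H patients will be enrolled. The criteria allow it; they do not make it certain.
- That monotherapy Part 2A has the same fault. Its row carries the same label, but the documents give no reason to expect MSI-driven responses to BMS-986207 alone.

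**What to change.** 1. In Section 10.1.3.1 and Tables 10.2-1 and 10.3.1-1, state that the Part 2B CRC response counts (7 and 15) are made in participants with confirmed non-MSI-H/MMR-proficient tumours, using the status already collected under Section 6.1 2)j. Part 2C already does this kind of thing with its NSCLC efficacy set.
2. Report MSI-H/dMMR participants separately, and keep the all-treated ORR alongside so that Section 10.3.1 is still honoured.
3. Align the CRC eligibility text with the design population, or state that the FPR applies only to the non-MSI-H set.

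The same set may be used in Part 2A for consistency only.

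With this change the FPR is 2.6-3.5% and the claim holds. The text cost is a few lines, and the SAP is not final until before database lock. The real cost is fewer than 15 counted participants if any MSI-H patient is treated. Losing one from stage 2 moves the two-stage FNR from 9.7% to 1 − [0.6706 + 0.2471 × (1 − 0.7^7)] = 10.3%, so the sponsor should say whether such participants are replaced. If eligibility is restricted, MSI/MMR results are needed before dosing and a few candidates are lost.
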